4. STATISTICAL METHODS

For continuous variables, means, medians, ranges, and standard deviations will be presented. For categorical variables, the number and percentage of patients within each category will be presented. For each variable (continuous or categorical), the number of available observations will be reported. No formal hypothesis testing will be performed as the study is entirely descriptive.

4.1 OUTPUT LAYOUTS

The key output layout is designed to address the study objectives in a flexible manner and provide an overall view of the efficacy and safety of emicizumab for all dosing regimens. The key output layout is as follows:

All patients: these outputs will provide an overall view of all the data collected under emicizumab prophylaxis. Patients will be grouped according to their original maintenance regimen at study entry (QW, Q2W and Q4W) with a total column provided as well.

Listings will include all the data for all the patients with a flag indicating the dose related to each event and the dosing regimen of the patients. As appropriate, outputs will be produced for each dosing regimen separately.

Patients may be allowed to up-titrate their emicizumab dose if they meet the pre-specified criteria as described in the protocol. Patients will be grouped according to their original maintenance dose at study entry.

The data under the new, higher dose will be analysed and reported separately. Additional summaries will be produced for key safety and exposure on all data (i.e., data before and after up-titration).

For Cohort A, the primary set of outputs will include patients from 0 to < 12 years of age. Three additional limited sets of outputs will be produced: one for patients \geq 12 years of age, one for the combined sets (0 to < 12 years of age and \geq 12 years of age) and one for patients \leq 2 years old at time of enrolment.

For Cohorts B and C, only one set of outputs will be produced for each cohort and will include all the patients enrolled in these cohorts.

4.2 ANALYSIS POPULATIONS

4.2.1 All Patients

All patients' population includes all patients enrolled in the study.

4.2.2 Treated Population

Treated population corresponds to all patients who received at least one dose of emicizumab. This population will be the primary population for efficacy and safety analyses.

4.2.3 Non-Interventional Population

This population includes patients who participated in Cohort B of the NIS BH29768 prior to enrolment to this study. All the NIS patients enrolled in BH29992 are enrolled to Cohort A.

4.2.4 Pharmacokinetic-Evaluable Population

The PK population includes all patients who have received at least one dose of emicizumab and have at least one post-dose emicizumab concentration result.

4.2.5 Patients 12-17 Years of Age Who Weigh <40 kg

This population includes patients 12-17 years of age who weigh < 40 kg at the time of informed consent.

4.2.6 Patients \leq 2 Years of Age

This population includes patients \leq 2 years of age at the time of informed consent.

4.2.7 Up-titrated Patients

This population includes patients who had at least one dose up-titration.

4.3 ANALYSIS OF STUDY CONDUCT

The flow of patients through the study will be displayed in a 'CONSORT' diagram. A clear account of all patients who entered the study, who were enrolled, who dose up-

titrated, and who completed each period of the study will be displayed. In addition, reasons for premature discontinuation from study treatment and reasons for withdrawing from the study (e.g., during follow-up) will be described.

Major protocol deviations will be summarized.

Observation time and duration of follow up, as well as adherence to planned assessment schedule and compliance with data entry into the electronic handheld device, will also be evaluated.

4.4 EFFICACY ANALYSIS

The efficacy objectives of this study will be investigated without any formal hypothesis testing. All analyses will be of descriptive nature only.

4.4.1 Efficacy Endpoint

4.4.1.1 Bleed Rate

A bleed is defined in two ways. The first definition uses adapted ISTH definition of a bleed ([Blanchette 2014](#); see Section [2.3.2.1](#); see Protocol Section 4.7.8). The second definition is counting all the bleeds regardless of the treatment (see Section [2.3.2.2](#)).

The number of bleeds over time (bleed rate) will be calculated using a negative binomial (NB) regression model, which accounts for different follow-up times, with time that each patient stays in the study (efficacy period) included as an offset in the model. In addition, the number of bleeds will also be annualized for each patient using the following formula:

$$ABR = (Number\ of\ bleeds/number\ of\ days\ during\ the\ efficacy\ period) \times 365.25.$$

For the interim CSRs, the population ABR may not be robust as it might be driven by only a few extreme observations because of the short follow up time. Therefore, the bleed rate will be characterized through individual patient data collected on the BMQ. In addition, with such short follow up, the NB model might not converge or the results might be unreliable. For all the patients, the number of bleeds will be described with use of descriptive statistics. The individual ABR will be calculated for patients who have been on the study for at least 12 weeks on the same dose (including the loading doses) with use of the given formula above.

The number of bleeds, types, and locations of bleed will be summarized for all patients and listed for each patient individually. Several exploratory analyses will be conducted to characterize the type, location, frequency, and pattern of bleeds.

4.4.1.2 Intra-Patient Comparison

The definition of treated bleeds and all bleeds is described in Section [2.3.2](#). The analysis methodology is the NB regression model.

This analytic model estimates the rate ratio, λ_t/λ_c , which quantifies the risk of bleeding associated with prophylactic emicizumab (λ_t) in comparison to the historical bleeding events (λ_c). The analysis will be performed overall and for each dose titration.

The treatment effect therein is based on a repeated statement in the model with use of the SAS GENMOD procedure. Bleed rates for prophylactic emicizumab and no prophylaxis and the rate ratio will be presented and include 95% confidence intervals.

The intra-patient comparison will be performed on patients who have been enrolled at least 12 weeks before the cut-off.

For the Interim CSR, individual patient's ABR will be provided in a descriptive manner including the reduction in ABR comparing before and after entering into Study BH29992. At this stage, the patients included in the analysis will have been on the study for at least 12 weeks.

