2.3.2.6 Intra-Patient Comparison

In the intra-patient comparison (on All Bleeds and on Treated Bleeds), only patients who participated in the NIS BH29768 are included. This is because it is possible to apply the detailed definition only if the data are collected with the same granularity for both time periods. Of note, for some patients who participated in NIS BH29768, the total time in that study prior to enrolment in Study BH29992 may be short.

The efficacy period in NIS BH29768 is defined as the time from the first entry on the electronic, handheld device or site data entry system to the day before the patient is enrolled in Study BH29992. Usually, the date of the first entry is the date the Training Module on the electronic, handheld device is completed.

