2.4 DETERMINATION OF SAMPLE SIZE

The sample size for this study is based on feasibility and clinical considerations rather than statistical considerations, taking into account the number of pediatric patients with hemophilia A with inhibitors available for participation in this trial. Hence, at least 40 children younger than 12 years of age and up to approximately 80 patients with hemophilia A and FVIII inhibitors who are currently receiving treatment with bypassing agents will be enrolled in this study: approximately 60 patients in Cohort A with allowance of patients 12-17 years of age who weigh < 40 kg at the time of informed consent and with allowance for approximately 5 additional patients < 2 years of age in Cohort A - and approximately 10 patients each in Cohort B and Cohort C.

During the study, a re-assessment of the initially specified sample size based on enrolment consideration may be performed. This may result in an increase in sample size, if necessary, to expand the safety database.

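### The SAP gives no standard-error type or small-sample correction for the intra-patient rate ratio; under the usual GEE default its 95% interval is likely too narrow, clearly so with about 20 or fewer NIS patients

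*SAP*

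**What the plan says.** SAP 4.4.1.2 sets the method: "The analysis methodology is the NB regression model". It adds that the treatment effect is "based on a repeated statement in the model with use of the SAS GENMOD procedure". The output is also specified: "Bleed rates for prophylactic emicizumab and no prophylaxis and the rate ratio will be presented and include 95% confidence intervals". The comparison is to be run overall and again by dose titration.

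SAP 2.3.2.6 defines who enters: "only patients who participated in the NIS BH29768 are included". SAP 4.2.3 places them: "All the NIS patients enrolled in BH29992 are enrolled to Cohort A". SAP 2.4 gives the size of that cohort, "approximately 60 patients in Cohort A", with room for about 5 more children under 2 years. Neither document says how many Cohort A children came from the NIS.

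The SAP's warning about small samples (4.4.2) is attached to the subgroup analyses. Its caution about short follow-up (4.4.1.1) is attached to the interim reports. Protocol 6.4.1 falls back to the ABR if the negative binomial model fails to converge. None of these deals with the coverage of the interval in 4.4.1.2.

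**The concern.** A REPEATED statement fits a generalised estimating equation (GEE) with the patient as cluster. In common practice its interval is the empirical sandwich standard error times 1.96. That standard error is biased low when clusters are few, because each patient's residual is pulled towards zero by that patient's own influence on the fit. The normal quantile also ignores the uncertainty in the variance estimate. Both errors make the interval too short.

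The comparison with the patient's own earlier bleeding is a named efficacy objective (Protocol 2.1, SAP 2.3.2). As no hypothesis is tested, the interval is the only stated measure of how well the ratio is known. If its real coverage is well under 95%, the report claims more precision than the data give.

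**Working it through.** **No planned figure to reproduce.** The documents give no sample size, power or precision for this analysis. The only stated figure is the nominal 95%, so the check is on coverage.

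**Inputs from the documents**
- Negative binomial model, REPEATED statement, 95% interval: SAP 4.4.1.2.
- Number of clusters: not stated; ceiling about 60 + 5 = 65 (SAP 2.4, 4.2.3).
- Follow-up in the NIS: possibly over 24 weeks (Protocol 3.1), but short for some (SAP 2.3.2.6).
- Entry threshold for episodically treated patients: ABR of 6 or more (Protocol 4.2).

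**Assumptions (not in the documents)**
- Default empirical standard error, normal quantiles, independence working correlation.
- NIS follow-up 12-30 weeks; on-study follow-up 26-60 weeks.
- Scenario 1: historical ABR 12, rate ratio 0.15, dispersion 0.8 before and 2 on study.
- Scenario 2: historical ABR 12, rate ratio 0.05, dispersion 0.8 before and 4 on study.
- Scenario 3: historical ABR 18, rate ratio 0.2, dispersion 0.5, one frailty shared by both periods.

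**Formulas.** For patient i in period p, with count y, follow-up T, mean mu = T·exp(b_p) and dispersion k estimated by maximum likelihood:
- weight w_ip = mu/(1 + k·mu); A_p = sum of w_ip; leverage h_ip = w_ip/A_p
- influence psi_ip = [(y − mu)/(1 + k·mu)]/A_p
- uncorrected: SE = sqrt(sum over i of (psi_i,on − psi_i,hist)²); interval = estimate ± 1.96·SE
- corrected (Mancl-DeRouen): replace psi_ip by psi_ip/(1 − h_ip); interval = estimate ± t(n−1)·SE

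**Results.** Coverage in %, with 1,500 runs per cell up to n = 20 and 1,000 above (Monte Carlo error about 0.6-1.0 points):

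| n | Uncorrected, scenarios 1 / 2 / 3 | Corrected, scenarios 1 / 2 / 3 | Width ratio (log scale) |
|---|---|---|---|
| 6 | 83.0 / 89.1 / 85.1 | 96.4 / 96.5 / 95.7 | 1.58 |
| 8 | 87.0 / 91.2 / 87.7 | 95.0 / 97.7 / 95.4 | 1.38 |
| 10 | 87.9 / 92.2 / 88.2 | 94.3 / 97.7 / 94.4 | 1.28-1.29 |
| 15 | 89.1 / 88.4 / 90.3 | 93.8 / 94.1 / 94.6 | 1.17 |
| 20 | 90.0 / 90.6 / 92.3 | 93.3 / 94.1 / 94.3 | 1.12-1.13 |
| 30 | 93.1 / 91.9 / 93.8 | 94.9 / 93.2 / 95.2 | 1.08 |
| 40 | 92.0 / 90.7 / 94.2 | 93.5 / 91.7 / 96.0 | 1.06 |
| 60 | 92.8 / 93.8 / 95.0 | 93.7 / 94.2 / 96.1 | 1.04 |

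Runs with no bleeds in one period were excluded: in scenario 2, 21.2% at n = 6, 11.8% at n = 8, 6.5% at n = 10 and 2.1% at n = 15; at most 1.9% in every other cell.

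**Check on the width ratio.** With roughly equal leverages it should be (t/1.96) × n/(n − 1). At n = 20: (2.093/1.96) × 20/19 = 1.068 × 1.053 = 1.12. At n = 60: (2.001/1.96) × 60/59 = 1.021 × 1.017 = 1.04. Both agree with the table.

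**Sensitivity to the assumptions.** A second set used a historical rate of 15 per year (dispersion 0.6), 0.5-2 per year on study (dispersion 1-3) and within-child correlation 0.5, with 600 runs per setting. Uncorrected coverage was 81-94% at n = 8-20 and 92-94% at n = 30-50; corrected, 92-98% and 93-96%. A third set, with on-study time matched to the 52-week timing of the primary analysis, gave 83-92% at n = 8-20 and 91-94% at n = 30-60; corrected, 91-97% and 92-95%.

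**The case against.** The strongest reply is that the premise is not in the documents. The SAP mentions only a REPEATED statement, so an uncorrected sandwich interval is inferred from silence. The NIS number is not given, so the subset cannot be called small. Near the ceiling the shortfall is minor: 92.8-95.0% at n = 60. All of this stands, and the point has to be conditional on n and on the standard error used.

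Three stronger readings might also be inferred, and none is supported:
- That the 12-week enrolment rule in SAP 4.4.1.2 shrinks the sample. The primary analysis is timed 52 weeks after the last patient of Cohort A's primary population enters (SAP 2.5). The rule therefore removes none of that population and could touch only late-enrolled children under 2.
- That this is the trial's only comparative efficacy estimate. SAP 4.4.2 plans comparative subgroup analyses and SAP 2.3.2.7 plans an up-titration analysis.
- That the correction guarantees 95%. In scenario 2 it gives 91.7% at n = 40. In one setting of the second set at n = 20, coverage moves from 93.7% to 96.3%, as far above nominal as it was below.

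The practical effect is also limited. The study is declared descriptive (SAP 4), and efficacy rests partly on extrapolation from adults (Protocol 3.3). In a rerun with on-study rate 2 per year and dispersion 3, the correction moved the median upper limit of the ratio from 0.25 to 0.28 at n = 20 and from 0.21 to 0.22 at n = 50. No reader would change the interpretation on that.

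What remains is that the error runs towards overstated precision in nearly every cell, and that the cost of the correction falls as n grows. Not knowing n is a reason to specify the correction in advance.

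**Conclusion.** The point holds in conditional form. If SAP 4.4.1.2 is run with the empirical standard error and normal quantiles, the nominal 95% interval for the intra-patient ratio likely covers about 81-94% of the time with 20 or fewer NIS patients and about 91-95% with 30-60. The exposure is greatest in the analyses by dose titration, which have fewer patients than the overall comparison.

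The documents do not support saying outright that the interval is too narrow or that the subset is small. The figures rest on assumed rates, dispersions, follow-up and software default, and at the lowest n in scenario 2 on the exclusion of runs with an empty period. This is an inexpensive improvement to the plan and puts no conclusion of the trial in doubt.

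**What to change.** In SAP 4.4.1.2:
- Keep the negative binomial GEE, and state the working correlation and the standard-error type.
- Specify a bias-corrected empirical variance, for example Mancl-DeRouen, with t quantiles on the number of patients minus 1 degrees of freedom.
- Report the number of NIS patients beside each ratio, overall and by titration.
- For very small titration groups, show individual ABRs instead of a model interval. The SAP already does this for the interim report. Set the minimum number of patients before the data are seen.

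The cost is a few sentences in the SAP and possibly some extra coding, since the correction may need a different procedure or a short macro. No new data and no design change are needed. Under strong dispersion coverage improves but may stay slightly below 95%, and the report should say so.

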4.4.1.3 Health-Related Quality of Life (HRQoL)

For Haemo-QoL-SF, descriptive analyses including summaries and 95% confidence intervals of change from baseline for each individual subscale and the overall score will be performed. Individual patient plots of the overall score at each timepoint will be generated. For the interim CSRs, individual patient plots will be performed, and if at least 8 patients have been on the study for at least 12 weeks, the descriptive analysis including summaries and 95% confidence intervals will be performed. Note that the number of patients contributing to the analysis is very limited because the questionnaire is completed only by a subset of patients (those 8 years of age and above).

For aspects of caregiver burden using Adapted InhibQoL including Aspects of Caregiver Burden questionnaire for all children (completed by caregivers), descriptive analyses and 95% confidence intervals of change from baseline for each individual subscale will be performed. Individual patient plots of the overall score at each timepoint will be generated. For the interim CSRs, individual patient plots will be performed, and if at least 8 patients have been on the study for at least 12 weeks, the descriptive analysis including summaries and 95% confidence intervals will be performed.

Number of days of missed day care/school and days hospitalized will be analyzed using descriptive statistics and 95% confidence intervals. For the interim CSR, if at least 8 patients have been on the study for at least 12 weeks, the descriptive analysis including summaries and 95% confidence intervals will be performed.

The Week 12 timepoint has been chosen because the patients/caregivers are completing the QoL questionnaires every 12 weeks. Therefore at least 1 questionnaire in addition to baseline should have been completed for these patients.

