4.7.2 Medical History and Demographic Data

Medical history includes hemophilia-related history, clinically significant diseases, procedures within the past year, and medication allergies. In particular, sites should record whether the patient has any history of prior ITI, anaphylaxis, or known thrombophilia. It should also include all medication taken in the 4 weeks prior to screening (including prescription, over-the-counter, and herbal/homeopathic remedies and therapies), see Section 4.6 for details. Bleed information (i.e., number, type) should be documented during the last 24 weeks prior to study entry. Number of daycare/school days missed and number of days hospitalized should be documented prior to study entry.

Demographic data will include age, sex, and self-reported race and ethnicity (as per specific country regulations).

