6.7 PATIENT-REPORTED OUTCOME ANALYSES

Scale scores for the Haemo-QoL-SF and the Adapted InhibQoL Including Aspects of Caregiver Burden will be calculated for each assessment, with change scores being examined for the assessments over the course of the study. These will be summarized descriptively by cohort. A descriptive summary of the number of daycare/school days missed and days hospitalized will also be presented by cohort.

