The Physical Health domain consists of five questions focused on the child's hemophilia-related symptoms (bruises, bleeds, painful swellings, presence of joint pain and joint stiffness) and two questions on physical functioning limitations (pain with movement, sleep through the night because of pain) because of hemophilia. Two other domains cover issues related to the burden on caregivers of dealing with a child with inhibitors. The Dealing with Inhibitor domain includes questions on the psychological impact (anxiety, fear and worry) associated with their son's hemophilia A. Additionally, the Perceive treatment domain includes questions focused on the impact that treatment has on the caregiver in terms of the interference with daily life, difficulty in preparing the injections, and satisfaction with the amount of time to administer treatment. These three domains are of particular interest given the consistency with the Haemo-QoL-SF (for Physical Health) and the potential reduction in burden as a result of emicizumab treatment.

- Assess the number of days missed from daycare/school (completed by caregivers) and days hospitalized

Caregivers will be asked to report as per the schedule of assessments the number of days of daycare/school that were missed and this will be completed following the Adapted InhibQoL including Aspects of Caregiver Burden questionnaire. The number of days the child was hospitalized (if applicable) will be derived from data collected on eCRF.

Of note, the Haemo-QoL-SF, caregiver-reported HRQoL, and aspects of caregiver burden questionnaires are completed every 3 months from the Week 1 assessment and request inputs from the past 4 weeks.

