Appendix 2 Schedule of Assessments (cont.)

- ^q Patients are advised to inform the investigator about adverse events at every visit. Adverse events will be reported on the eCRF by the investigator. Injection-site reaction adverse events will be collected on a separate form from the adverse event form. If there is unexpected worsening of the patient's hemophilia in terms of severity (e.g., increased number of doses of bypassing agents to stop bleeds compared with before study entry), frequency of bleeds, or nature at any time during the study, this should be documented as an adverse event on the Adverse Event eCRF, conveying that the underlying condition has changed by including applicable descriptors (e.g., "increased clinical severity of hemophilia").
- ^r Drug accountability will not be performed at the first visit of emicizumab receipt. Drug dispensation will not occur at the study completion/early termination visit. *Note: for Cohort C, there are visits where emicizumab is not administered per schedule.*
- ^s Haemo-QoL-Short Form (children 8 years of age and older) assessed on an electronic, handheld device by patients during patient's visit in clinic prior to emicizumab injection at Weeks 1, 13, 25, 37, 49, every 24 weeks from Week 57, and study completion/early termination.
- ^t Proxy assessment of HRQoL and aspects of caregiver burden using the Adapted InhibQoL Including Aspects of Caregiver Burden questionnaire for all children assessed on electronic, handheld device by caregivers during patient's visit in clinic prior to emicizumab injection at Weeks 1, 13, 25, 37, 49, every 24 weeks from Week 57 and study completion/early termination.
- ^u Emicizumab concentration. Plasma samples for this assessment should be taken prior to emicizumab injection.
- ^v PD biomarkers will be measured at a central laboratory. See [Appendix 3](#), for detailed explanation of PD biomarker assessments. Blood samples may also be drawn to conduct biomarker assays at the central laboratory on an unscheduled basis (at the clinical judgment of the investigator) at any time.

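### Hospital days and missed daycare/school days are summarised by cohort as raw counts without a time denominator, although Cohort A is followed at least about twice as long as Cohorts B and C

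*SAP*

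**What the plan says.** Days missed from daycare or school and days hospitalised form one of the efficacy objectives in Protocol 2.1. Protocol 6.4.2 places them under exploratory efficacy endpoints.

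- **Summary measure.** SAP 4.4.1.3: "Number of days of missed day care/school and days hospitalized will be analyzed using descriptive statistics and 95% confidence intervals". Protocol 6.7: "A descriptive summary of the number of daycare/school days missed and days hospitalized will also be presented by cohort". SAP 4.1 groups outputs by original regimen and adds a total column. No denominator, offset or annualisation is given for these two counts.
- **Source of missed days.** Caregivers report them on the site tablet. SAP 2.3.3 says of this item: "this will be completed following the Adapted InhibQoL including Aspects of Caregiver Burden questionnaire".
- **Recall and frequency.** For the Haemo-QoL-SF and the caregiver instruments, SAP 2.3.3 says that the "questionnaires are completed every 3 months from the Week 1 assessment and request inputs from the past 4 weeks". The missed-day item is not named in that sentence. SAP 2.2 gives a quarterly frequency and does include the item; Protocol 3.1 gives 12-weekly. Both refer to the schedule of assessments. In SAP Appendix 2 the Haemo-QoL-SF footnote reads "at Weeks 1, 13, 25, 37, 49, every 24 weeks from Week 57, and study completion/early termination", and the Adapted InhibQoL footnote lists the same visits. The schedule has no row for missed days.
- **Source of hospital days.** They are derived from eCRF data (SAP 2.3.3, Protocol 4.7.7).
- **Follow-up.** The primary analysis is timed 52 weeks after the last enrolment into the primary population of Cohort A (SAP 2.5). Protocol 3.1 expects an efficacy period of about 6 months in Cohorts B and C. Patients under 2 years who enrol late in Cohort A are included whatever their follow-up (SAP 2).
- **Contrast.** SAP 4.4.1.1 analyses bleeds with the efficacy period as an offset and also annualises them per patient.

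**The concern.** A number of days accumulates with time observed. When groups are observed for different lengths of time by design, a mean number of days per patient mixes the event rate with the length of follow-up. The 95% confidence interval around it then describes a quantity that is not comparable between cohorts. The plan deals with this for bleeds and not for these two counts.

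The risk is one of reading. Columns for the weekly, 2-weekly and 4-weekly regimens would stand side by side, and a reader could take a twofold difference in hospital days for a difference between regimens. The same applies on a smaller scale within Cohort A, where late-enrolled infants and early withdrawals sit beside children followed for more than a year, and in the total column, which averages over all of these durations.

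**Working it through.** The documents give no figure for these endpoints, so there is nothing to reproduce. The check is how far follow-up alone moves a raw count.

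**Inputs**
- Cohort A follow-up: 52 weeks, a lower bound for patients in the primary population who have not withdrawn (SAP 2.5).
- Cohorts B and C: about 6 months (Protocol 3.1), taken as 26 weeks.
- Post-baseline questionnaires: Weeks 13, 25, 37 and 49, then every 24 weeks from Week 57 (SAP Appendix 2, Adapted InhibQoL). Week 1 is before the first dose and is left out.
- Recall for the missed-day item: not stated. The range used is 4 weeks (as for the questionnaires) to 12 weeks (the interval between visits).
- Assumption: the same true rate r in all cohorts.

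**1. Hospital days.** Expected days per patient = r × weeks observed.
- Ratio A to B/C = (r × 52)/(r × 26) = 2.0.
- This is a lower bound for most of Cohort A. By Protocol 3.3.1.1 the first 20 patients were in by the 28 October 2016 cutoff, and enrolment continued after 7 December 2016, which is 40 days or 5.7 weeks later. Unless withdrawn, those 20 have at least 52 + 5.7 = 57.7 weeks, and 57.7/26 = 2.2.
- If Cohort A follow-up were 76 or 100 weeks (assumed values), the ratio would be 76/26 = 2.9 or 100/26 = 3.8.

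**2. Missed days, if added up over visits.** Expected days per patient = r × weeks covered by recall.

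| Recall | A at 52 weeks | B/C at 26 weeks | Ratio |
|---|---|---|---|
| 4 weeks | 4 × 4 = 16 weeks | 2 × 4 = 8 weeks | 2.0 |
| 12 weeks | 4 × 12 = 48 weeks | 2 × 12 = 24 weeks | 2.0 |

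The ratio does not depend on the recall window. With 4-week recall and the assumed 76 or 100 weeks in Cohort A (five or six questionnaires) it is 20/8 = 2.5 or 24/8 = 3.0.

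**3. Is the cause recall coverage or follow-up length?** Share of time covered:
- 4-week recall: 16/52 = 31% in A and 8/26 = 31% in B/C.
- 12-week recall: 48/52 = 92% in A and 24/26 = 92% in B/C.

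The share is the same in both groups under either window, so the 2:1 ratio comes from the length of follow-up.

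**4. After normalising.** Hospital days divided by observed time give r in every cohort, a ratio of 1.0. Missed days at a given visit refer to the same recall window in every cohort, so the ratio is again 1.0.

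**The case against.** The strongest reply is that neither document says cumulative totals will be formed. Missed days are asked at fixed visits, and SAP 4.4.1.3 itself explains its 12-week interim threshold by the questionnaire visits. A by-visit summary is therefore at least as natural a reading, and by visit the cohorts are comparable. This stands for missed days, for which the 2:1 figure is conditional. It does not answer the point for hospital days, which have no questionnaire visit and no stated window.

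It can also be said that the study is descriptive ("No formal hypothesis testing will be performed as the study is entirely descriptive"), that Protocol 6.4.2 calls these counts exploratory, that no formal cohort comparison is planned, and that observation time and exposure will be reported (SAP 4.3 and 4.6.1). All of this stands and limits the weight of the point. Reporting follow-up in another table lets a careful reader see the imbalance but does not correct the estimate or its interval.

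A reader might infer more than the documents support:
- *That missed days are recorded for only a third of treatment time, and a sixth after Week 57.* The arithmetic is 4/12 = 33% and 4/24 = 17%. It holds only if the 4-week recall and the Adapted InhibQoL schedule both apply to the missed-day item, and neither is stated for it. With 12-week recall, coverage to Week 52 is about 92%. With 12-weekly visits after Week 57 and 4-week recall, coverage there would be 33%.
- *That recall coverage drives the cohort difference.* Step 3 of the working shows that it does not.
- *That hospital days are captured completely.* This is an inference from eCRF derivation. Protocol 5.3.5.11 exempts some admissions from adverse-event reporting, and the documents do not say whether those days are collected elsewhere. Incomplete capture at the same fraction in all cohorts would leave the ratio in step 1 unchanged.

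**Conclusion.** The point holds for the summary measure. As written, the plan reports unnormalised day counts by cohort, with 95% confidence intervals in the SAP, for cohorts whose follow-up differs at least about twofold at the primary analysis. For hospital days the expected distortion is about 2:1 at equal true rates, and more for Cohort A patients followed beyond 52 weeks. For missed days it is about 2:1 if they are added up, and absent if they are shown by visit; the SAP should say which.

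This rests on 26 weeks standing for about 6 months in Cohorts B and C, 52 weeks as the lower bound for most of Cohort A, and equal true rates. It does not rest on any recall window or on complete capture of admissions. The documents do not establish that the missed-day data are mainly an artefact of thin recall. The consequence is confined to descriptive interpretation of an exploratory endpoint; no test or sample size depends on it.

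**What to change.** In SAP 4.4.1.3:

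1. Report hospital days as a rate, for example per 28 days: total days divided by total observed time, times 28, by cohort and overall. Use a patient-level bootstrap interval or one from an over-dispersed count model with a time offset. If a cohort has no hospital days, a bootstrap interval has zero width, so report zero days with the observed time instead.
2. Report missed days by visit, per recall period, with the number of completed questionnaires at each visit. State the recall window of the item.
3. Do not show raw cumulative totals side by side across cohorts.
4. Reconcile the quarterly or 12-weekly frequency in Protocol 3.1, SAP 2.2 and SAP 2.3.3 with the 24-weekly schedule from Week 57 in the appendices, and add the missed-day item to the schedule.

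The cost is SAP wording and a denominator in tables already planned, plus a schedule clarification. No new data are needed.
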